## **3.2. Exclusion Criteria**

- 3.2.1. Prior radical surgery (prostatectomy), high-intensity focused ultrasound (HIFU) or cryosurgery for prostate cancer
- 3.2.2. Prior hormonal therapy, such as LHRH agonists (e.g., goserelin, leuprolide), antiandrogens (e.g., flutamide, bicalutamide), estrogens (e.g., DES), or bilateral orchiectomy
- 3.2.3. Use of 5-alpha reductase inhibitors (finasteride, dutasteride) specifically prescribed for the treatment of prostate cancer.
- 3.2.4. Prior or concurrent cytotoxic chemotherapy for prostate cancer; prior chemotherapy for a different cancer is permitted.
- 3.2.5. Prior radiation, including brachytherapy, to the region of the prostate that would result in overlap of RT fields.
- 3.2.6. Active lupus or scleroderma

3.2.7. Severe, active co-morbidity, including but not limited to:

- 3.2.7.1. Unstable angina within the last 6 months without subsequent corrective cardiovascular procedure.
- 3.2.7.2. Acute bacterial or fungal infection requiring intravenous antibiotics at the time of registration.
- 3.2.7.3. Hepatic insufficiency with AST, ALT, or Bilirubin > 2 x upper limit of normal, clinical jaundice, and/or coagulation defects
- 3.2.7.4. Acquired Immune Deficiency Syndrome (AIDS) based upon current CDC definition; note, however, that HIV testing is not required for entry into this protocol. Patients who are HIV seropositive but do not meet criteria for diagnosis of AIDS are eligible for study participation.

### **3.3. Inclusion of Minorities and Women**

All races and ethnic groups are eligible for this trial. Women are not eligible as the natural history and epidemiology of prostate cancer is such that only men develop the disease.

## **4. TREATMENT PLAN**

### **4.1. Dual Oral Androgen Manipulation**

Treatment will be administered on an outpatient basis. Reported adverse events and potential risks are described in Section 6.

After study enrollment, patients will initiate dual oral androgen manipulation therapy consisting of an androgen receptor blocker and a 5AR inhibitor according to the following dose and route schedules:

- Bicalutamide 50 mg PO daily
- Dutasteride 0.5 mg PO daily (recommended) or Finasteride 5 mg PO daily

During week 6-8 of oral androgen manipulation therapy, patients will undergo CT simulation for radiation planning. After 8 weeks of hormonal therapy, patients will begin dose escalated radiation with concurrent androgen manipulation for approximately 7-8 weeks, Monday through Friday. Details regarding planning and administration of RT are described in Section 5.

Following completion of radiation, having completed 4 total months of dual androgen manipulation, patients will discontinue Bicalutamide. All patients will continue taking the 5AR inhibitor as monotherapy for 2 years after completion of radiation for a total of 2 years, 4 months of treatment.

### **4.2. Measuring Health-Related Quality of Life and Toxicity**

Patient-reported outcome measures will include a modified version of the Expanded Prostate Cancer Index Composite (EPIC-26) which has been validated as an alternative to the complete questionnaire (EPIC-50).[33] The questionnaire will include all EPIC-26 items as well as additional items in the hormonal/vitality domain drawn from the full length EPIC-50. General

health-related quality of life, including fatigue, will be assessed with the PROMIS v1.0 Global short form and the EQ-5D visual scale for quality of life. All items will be consolidated into 2 questionnaires. The first questionnaire is the standard questionnaire administered to all patients with prostate cancer in the department of radiation oncology (see Appendix A). A supplemental four page questionnaire will be administered to all patients on trial and to all consenting control patients at baseline (see Appendix B). Both questionnaires will again be administered at 1-2 months after initiation of hormonal treatment (before RT), at 3-4 months (during RT), and at 6 months after initiation of study therapy. Questionnaires will be completed in writing by the patient. Questionnaires at 12, 18, and 24 months after completion of radiation therapy will not be required, although any collected data over this time frame will be recorded and available for analysis.

The evaluation period of acute radiation-related toxicity will be defined by the period from the start of radiation to three months following the completion of radiation. Toxicity will be graded according to Radiation Therapy Oncology Group (RTOG) acute toxicity scale (see Appendix D). Toxicity will be recorded on a weekly basis during radiation treatment and at the first follow up visit. Chronic toxicities will also be graded according to the RTOG toxicity scale and will be recorded at each point of clinical contact beyond the third month after completion of radiation.

#### **4.3. Experimental Controls**

Patients who meet eligibility criteria of the study but who do not enroll on the trial who receive standard ADT with radiation will be approached for participation in the parallel data collection study. These patients will serve as the control group with which to compare HRQOL outcomes of patients treated on trial. Patients consenting to enrollment on the parallel data collection study will receive standard of care treatment, follow-up, imaging, and laboratory studies not subject to the plan described in this protocol. Health information may be recorded from the electronic medical record. Patients on the data collection study will be asked to complete the same supplemental four-page questionnaire (see Appendix B) as those on trial at baseline, 1-2 months after initiation of standard ADT (before RT), and at 6 months. Completion of the supplemental questionnaire will not be required at 12, 18, and 24 months after initiation of radiation, however any collected data over this time frame will be recorded and available for analysis. In addition, all controls will complete the six-page questionnaire which is standard practice for all patients treated in the department of radiation oncology according to usual practice.

#### **4.4. General Concomitant Medication and Supportive Care Guidelines**

Development of painful mastitis and gynecomastia are potential side effects of antiandrogen therapy in the absence of gonadal suppression. There is no restriction towards the use of radiation for the prophylaxis or treatment of breast tenderness or gynecomastia. Patients should not receive Tamoxifen or other estrogen modulating therapy during treatment on the trial given concern for unknown effects on the hormonal milieu. Treatment with breast radiation to breast tissue should be clearly documented for each patient in whom it is employed. If prophylactic or therapeutic intervention is sought, a dose of 12 Gy in 3 fractions using en face electrons is preferred.

#### **4.5. Duration of Therapy**

Duration of dual oral androgen manipulation will be 4 months in all patients. The duration of 5AR inhibitor use will be 2 years, 4 months. Radiation therapy should be delivered over the course of 7-

8 weeks (Monday through Friday) beginning after the initial 8 weeks of oral androgen manipulation. Treatment delays should be avoided unless:

- Intercurrent illness prevents further administration of treatment
- There are unacceptable adverse event(s)
- The patient decides to withdraw from the study, or
- General or specific changes in the patient’s condition render the patient unacceptable for further treatment in the judgment of the investigator.

The use of continued treatment with 5AR beyond 2 years, 4 months is at the discretion of the treating physician.

#### 4.6. Duration of Follow Up

Patients will be followed on protocol through the completion of therapy (2 years after completion of radiation therapy). Beyond this time point, further data collection will be at the discretion of the treating physician. It is encouraged to continue follow-up every six months until 5 years after completion of radiation therapy, and monitor serum PSA over each of these visits, according to standard practice.

#### 4.7. Criteria for Removal from Study

Patients will be removed from the study when any of the criteria listed in Section 4.5 applies. The reason for study removal and the date the patient was removed must be documented in the Case Report Form.

#### 4.8 Registration Procedures

- Guidelines for the Lead (University of Chicago):  
All patients should be registered by the responsible Clinical Research Associate and or Research Nurse in the Velos Database after consent and prior to the start of treatment. The appropriate eligibility criteria in 3.1 should be confirmed prior to registration.

#### 4.9 Tissue Collection

For patients consenting to tissue collection portion of the study, the first block of FFPE tissue will be taken from the left over samples of Prostate biopsy done at initial diagnosis. If the patient has more than one diagnostic biopsy then tissue will be taken from the most recent biopsy sample.

A research biopsy will be collected at the time of intra-prostatic fiducial marker placement, after the initial 2 months of hormonal therapy. The marker placement is considered standard of care therapy, using a transrectal ultrasound probe (similar to the approach for a prostate biopsy). The biopsy would include patients in both treatment and control group. If the patient has had prior MRI, these images can be fused to the ultrasound using software (UroNav) which will increase the yield of the biopsy for tumor. The tissue collected will be stored at HRTC.

The following tables outline the requirements for tissue banking. Tissue will be collected and stored for batched future analysis.

Biospecimen Type	Collection time point	Number of samples
------------------	-----------------------	-------------------

A paraffin embedded tissue block of primary prostate cancer taken at initial diagnostic biopsy (left over sample)	Pretreatment, before starting any hormonal therapy	1 block
2 cores of paraffin embedded tissue of tumor	After 2 months of hormonal therapy at the time of fiducial marker placement , for consenting patients	2 blocks of FFPE

Tumor biopsy for molecular analysis will be conducted. Either fresh tissue or archived paraffin embedded specimens will be used for analysis. RNA from tumor samples will be isolated using standard techniques. We would like to 1) analyze intra-patient differences in RNA expression at initial biopsy specimen and after two months of hormonal therapy, and 2) compare the inter-patient differences in RNA expression in the oral ADT cohort versus the traditional injectable ADT cohort to test the hypothesis that oral-only ADT results in a similar RNA expression profile to traditional therapy.

## 5. RADIATION THERAPY GUIDELINES

### 5.1. Treatment Planning Procedures

5.1.1. Placement of fiducial markers in the prostate gland (e.g. gold markers) for image guidance is recommended but not required.

5.1.2. Simulation will be CT-based in all cases. The use of urethral contrast at the time of simulation is recommended but not required. Patients will be positioned supine on a flat tabletop with a customized thermoplastic immobilization cast or a molded foam cradle for stabilization and setup reproducibility.

### 5.2. Dose Specifications: 3D Conformal Radiotherapy (3DCRT) or IMRT

The prostate and seminal vesicles will be treated to a dose of 50-50.4 Gy in 1.8-2 Gy fractions prescribed to the PTV1. Subsequently, the prostate and any additional gross disease will be treated to a cumulative total dose of 75.6-79.2 Gy in 1.8-2 Gy fractions prescribed to the PTV2. The PTV2 prescription dose may be reduced to 72 Gy at the discretion of the treating radiation oncologist only if it is felt that critical structure dose constraints cannot be met for that particular case at a prescription dose of 75.6-79.2 Gy. All attempts should be made to deliver the dose with the heterogeneity constraints and adherence to the critical structure parameters listed below in Table 1. If 3DCRT is used, more relaxed rectal and bladder constraints are acceptable, but the rectal V70Gy must be  $\leq 20\%$  in all cases.

### 5.3. Suggested Critical Structure Dose Constraints

Table 1.

Target or Tissue (priority)	Parameter	Target
PTV (++++)	V100% (%)	$\geq 95\%$
	V95% (%)	$\geq 98\%$
	V105%*	$\leq 10\%$

	V110%*	≤ 5%
	Max dose to voxel	≤ 115%
Rectum (+++)	V70Gy (%)	≤ 10%
	V65Gy (%)	≤ 20%
	V40Gy (%)	≤ 40%
Bladder (++)	V70Gy	≤ 15%
	V65Gy	≤ 30%
	V40Gy (%)	≤ 60%
Femoral heads (+)	V50Gy (%)	≤ 10%
Penile bulb (++)	V50Gy	≤ 50%

#### 5.4. Technical Factors

RT will be delivered with megavoltage equipment at energies  $\geq 6$  MV.

#### 5.5. Treatment Planning/Target Volumes

The definition of volumes will be in accordance with the ICRU Report #50: Prescribing, Recording, and Reporting Photon Beam Therapy.

- 5.5.1. The recommended CTV1 includes the entire prostate gland and the proximal 2 cm of the seminal vesicles. In general, it is recommended that patients with intermediate risk disease and no evidence of seminal vesicle involvement should have at least the proximal 1.0 cm of seminal vesicles included in the target volume. The entire seminal vesicles should be included for any patients who have prostate cancer involving any portion of the seminal vesicles.
- 5.5.2. The CTV2 is defined by the physician as the entire prostate gland. If there is seminal vesicle involvement, it is recommended to include the entire seminal vesicles. If the rectal V70Gy  $\leq 20\%$  cannot be met, then the uninvolved portion of the seminal vesicle may be excluded from the final CTV2 volume.
- 5.5.3. The Planning Target Volume (PTV1) will provide a margin around the CTV1 to compensate for the variability of treatment set up and internal organ motion. A range of 5-10 mm around the CTV1 is required to define the PTV1. Superior and inferior margins (capping) should be 5-10 mm depending on the thickness and spacing of the planning CT scan. Careful consideration should be made when defining the 5-10 mm margin in 3 dimensions.
- 5.5.4. The Planning Target Volume (PTV2) will provide a margin around the CTV2 to compensate for the variability of treatment set up and internal organ motion. A range of 5-10 mm around the CTV2 is required to define each respective PTV. Superior and inferior margins (capping) should be 5-10 mm depending on the thickness and spacing of the planning CT scan. Careful consideration should be made when defining the 5-10 mm margin in 3 dimensions.

5.5.5. The ICRU Reference Points are to be located in the central part of the PTV and, secondly, on or near the central axis of the beams. Typically these points should be located on the beam axes or at the intersection of the beam axes.

5.5.6. Normal Critical Structures to be defined on the treatment planning CT scan will include the following: bladder (the outer bladder wall), rectum (from its origin at the rectosigmoid flexure to the inferior-most extent of the ischial tuberosities), bilateral femora (to the level of ischial tuberosity), penile bulb, and skin. Any small bowel within the primary beam aperture should be defined as well. All structures will be contoured in their entirety as solid organs.

5.5.7. A dose reduction to 72 Gy minimum PTV dose is permitted if the above constraints cannot be met at the planned dose level of 78 Gy. Of note, the penile bulb constraint is to be regarded as a suggested guideline, and adherence to this should not, in any way, result in compromised coverage of the dose delivery to the target volume.

## **5.6. Treatment Verification**

5.6.1. First day port films or orthogonal pair portal images must be obtained. Thereafter, weekly verification films or images of orthogonal isocenter views (anterior to posterior and lateral projection) are required. The use of daily image guided therapy (using fiducial markers or transabdominal ultrasound) is highly recommended.

5.6.2. For IMRT the intensity profiles of each beam must be independently verified and compared to the planned field intensity. Portal films are not required for IMRT but orthogonal verification films are required, just as for 3DCRT. These images are to be archived by the institution for later review if requested by the study chair.

## **6. RISKS AND BENEFITS**

The study will be fully explained to the subjects emphasizing the potential risks and benefits of their participation: the potential loss of their confidentiality with regards to their prostate cancer, the closer monitoring of their progress due to both research and medical staff working on their case, and the altruistic aspect of helping men in the future with prostate cancer. No monetary gain will be offered to the subjects and they will be informed that their decision will have no impact on the quality of care they will receive. The primary investigator will answer any and all questions in full. Subjects will be given a copy of the consent for their own records and will be given instructions as to how to withdraw from the study if they change their mind.

Medication and radiation side effects will be discussed with all patients. Adverse events will be monitored and reported.

### **6.1. Adverse Events**

#### **6.1.1. Dutasteride:**

Side effects of dutasteride may include serum testosterone increase, thyroid-stimulating hormone increased, impotence, libido decreased, ejaculation disorders ( $\leq 1\%$ ), gynecomastia, breast tenderness or pain, hypersensitivity (pruritus, rash, urticaria, swelling face/lips,

angioedema), dizziness, edema, diminished urinary flow, hepatic impairment. Pregnant women or women trying to conceive should not handle the product.

#### 6.1.2. **Finasteride**

Side effects of finasteride may include, impotence, decreased libido, neuromuscular or skeletal weakness, postural hypotension, edema, dizziness, somnolence, ejaculation disturbances, gynecomastia, dyspnea, rhinitis, hypersensitivity (pruritus, rash, urticaria, swelling face/lips), breast tenderness, testicular pain, and diminished urinary flow. Women should not handle finasteride as its active ingredient is absorbed through skin; pregnant women should not handle finasteride as it may negatively impact fetal development.

#### 6.1.3. **Antiandrogen (Bicalutamide)**

Side effects of antiandrogen therapy may include gynecomastia, breast tenderness or pain, hepatotoxicity (including rare cases of fatal hepatitis), inhibition of spermatogenesis, hot flashes, gastrointestinal disorders, diarrhea, nausea, weakness, pruritus, decreased libido, erectile dysfunction, and rash. Bicalutamide should be discontinued if ALT rises above two times the upper limit of normal or the patient develops jaundice.

#### 6.1.4. **Radiation**

Radiation side effects are limited to the area involved in the treatment field. Acute and late toxicity related to radiation therapy may include fatigue, skin erythema, diarrhea or loose stools, damage to the bowel or rectum (including stricture or obstruction, bleed, fistula formation, or perforation), radiation enteritis, dysuria, hematuria, increased urinary frequency, urethral stricture, urinary incontinence, decreased sexual function, and impotence.

### 6.2. **Reporting**

All life threatening Grade 4 or fatal toxicities (grade 5) must be reported immediately and evaluated.

- University of Chicago Reporting Guidelines:
  - If the reaction requires reporting, the Research Nurse or MD reports the adverse reaction to the Cancer Clinical Trials Office (CCTO) at [contact] by the end of the business day when he/she becomes aware of the event. Events occurring after business hours will be reported to the CCTO by 12 pm (noon) the next business day.
  - The following information is required when calling in the event:
    - Caller's Name and Telephone Number
    - Patient Initials
    - Patient Medical Record Number
    - IRB Protocol Number
    - PI of Study
    - Attending Physician
    - Date of Event
    - Description of Event (including grade of event and attribution of the event and if the event required hospitalization).
  - Email is sent to the research nurse, attending physician, and PI of the study informing them that adverse reaction notification has been received
  - The University of Chicago's IRB Serious Adverse Event Form must be sent to the CCTO within 5 calendar days of event occurrence. The UC IRB Serious Adverse Event form is available on line at <http://ors.bsd.uchicago.edu/HS/newirbforms>. This

form must be typed. Once the forms are completed, the original is forward to the study PI to review and sign. The signed report is delivered to the QA Coordinator. A weekly report of delinquent or pending documents will be forwarded to the applicable person who reported the event. All delinquent reporting (great than 10 days from the even occurrence) must include documentation of reason fro delinquency and may require implementation of an action plan.

- Once the appropriate AE documents have been received, the CCTO forwards these to the IRB. A copy will be forward to the appropriate Research Nurse.

### 6.3. Data and Safety Monitoring

A weekly meeting in the department of radiation oncology will be held for data and safety monitoring of patients enrolled at the University of Chicago site.

The primary endpoint, HRQOL, will be formally evaluated at 6 months.

Stopping rules include excessive failures defined by biochemical failure in > 70% of patients at 2 years or excessive toxicity defined as >15% of patients with acute or late Grade 3+ toxicity.

### 7. STUDY CALENDAR

Baseline evaluations (including performance status, history and physical, scans) are to be conducted within 60 days prior to the start of protocol therapy.

	Baseline	Month 2 (pre-RT)	Month 3-4 (during RT)	Month 6 (2 mos post- RT)	Month 10 (6 mos post-RT)	Month 16 (12 mos post-RT)	Month 22 (18 mos post-RT)	Month 28 (24 mos p RT)
Inclusion/ exclusion	X							
Informed Consent	X							
Path confirms cancer	X							
History and Physical	X	X	X**	X	X	X	X	X
Vital Signs, weight	X		X**	X	X	X	X	X
Zubrod Performance status and Charlson index	X							
Document Current Medicines	X	X	X**	X	X	X	X	X
CT Ab/Pelvis OR MRI*	X							
Bone Scan *	X							
Tumor tissue collection	X	X						
CBC with differential and CMP	X	X	X#	X		X		X
Toxicity Assessment			X**	X	X	X	X	X
Patient Outcome Questionnaire	X	X		X	X	X≠	X≠	X≠
PSA	X	X		X	X	X	X	X

Total, serum Testosterone	X	X				X		X
---------------------------	---	---	--	--	--	---	--	---

^ This evaluation will occur at the planning stage before radiation therapy has begun (e.g. fiducial marker placement or simulation)

\* See Section 3 for requirements/exceptions \*\* Weekly during radiation treatment

# These labs will be drawn in the last week of radiation therapy

≠ Optional

Note that the protocol allows for 1 month of flexibility to meet any follow-up appointment time (e.g. the month 6 visit may occur at month 5 or month 7.)

Beyond month 10, follow-up is recommended but not required. All data collected between month 10 and month 28 will be registered under this study so that longer term quality of life data (beyond the primary endpoint of 6 months) may be analyzed.

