## 8. MEASUREMENT OF EFFECT

### Disease Control

Although disease control is not the primary endpoint of this trial, patients will be assessed by standard criteria for disease response with serum PSA and clinical examinations. For the purposes of this study, patients should undergo serum PSA and testosterone testing at baseline, 2 months (at start of RT), and every three to six months until completion of androgen manipulation at 2 years, 4 months according to the study calendar. After completion of study treatment, it is recommended that PSA should be drawn every 6 months until 5 years post-treatment. Clinical exams should be performed on a regular basis at the discretion of the treating physician, but at least biannually during the course of therapy and at least annually thereafter. Screening for distant metastases will be based on clinical information and is at the discretion of the treating physician.

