### **9.3. Analysis of Secondary Endpoints**

As secondary endpoints, the study will investigate oncologic outcomes of the prescribed protocol therapy including biochemical progression-free survival, distant metastasis-free survival, cause specific survival, and overall survival. Kaplan-Meier curves will be generated for each endpoint. Findings will be compared to a synchronous cohort of controls.

Biochemical progression free survival will be defined to be the time from the start of therapy with oral androgen manipulation until PSA failure occurs as defined by the Phoenix definition of a rise to 2 ng/ml above the nadir PSA value. The relative hazard for a PSA failure in patients on protocol therapy compared to those in the control cohort will be calculated using the proportional hazards regression model of Cox, but formal statistical conclusions will not be drawn from this analysis.

Hematologic effects of dual oral androgen manipulation will be assessed using hemoglobin levels from scheduled CBC's. Changes in mean hemoglobin between baseline and various time points throughout treatment will be assessed. Univariate analysis of mean scores will be performed using a two sample t-test.

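### A note under the study calendar makes follow-up after month 10 voluntary, in conflict with section 4.6, section 8 and the calendar's own entries to month 28

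*Combined protocol and SAP*

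**What the plan says.** Four parts of the protocol set the length of follow-up for trial patients.

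- **Section 7, note under the calendar:** "Beyond month 10, follow-up is recommended but not required". The next sentence adds that data collected from month 10 to month 28 will still be registered, so that longer-term quality of life can be analysed.
- **Section 4.6:** "Patients will be followed on protocol through the completion of therapy (2 years after completion of radiation therapy", which is month 28 on the calendar. Only collection after that point is left to the treating physician.
- **Section 8:** PSA and testosterone should be tested at baseline, at the start of radiation, and then "every three to six months until completion of androgen manipulation at 2 years, 4 months according to the study calendar". Clinical exams are due "at least biannually during the course of therapy and at least annually thereafter".
- **Section 7, calendar body:** history and physical, current medicines, toxicity assessment and PSA carry a plain X at months 16, 22 and 28. CBC and testosterone carry one at months 16 and 28. Only the questionnaire row has the optional symbol.

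Three other parts depend on the answer. Treatment itself runs to month 28 (section 4.5: "The duration of 5AR inhibitor use will be 2 years, 4 months"). Section 6.3 has a stopping rule on "biochemical failure in > 70% of patients at 2 years" and another on acute or late Grade 3+ toxicity in more than 15% of patients. Section 9.3 plans analyses of "biochemical progression-free survival, distant metastasis-free survival, cause specific survival, and overall survival. Kaplan-Meier curves will be generated for each endpoint".

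**The concern.** A site can obey the calendar note and stop seeing a man at month 10, six months after radiation, while he still has 18 months of protocol 5AR inhibitor to take. The same site would then depart from section 4.6 and leave marked calendar entries empty. Nothing in the documents says which text governs, or how men who stop attending after month 10 are handled.

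The secondary objective and safety monitoring are at stake. PSA failure under the Phoenix definition needs a nadir and then a rise of 2 ng/ml, yet only two post-radiation PSA values (months 6 and 10) would be assured. Late toxicity is graded only when there is clinical contact. After month 10 the men still observed would be those who chose to come back, and their reasons for returning may be related to PSA or symptoms.

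**Working it through.** The plan states no figure for this point. Its one precision figure, plus or minus 15% for a success rate of 0.6 in 40 men (section 9.2), belongs to the hormonal/vitality score. It reproduces: 1.96 × √(0.6 × 0.4 / 40) = 15.2 points. The rest is coverage arithmetic followed by illustrations.

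**1. Timeline.** The calendar equates month 6 with 2 months after radiation, so radiation ends at about month 4. Two years later is 4 + 24 = month 28, which agrees with the 2 years 4 months of treatment in section 4.5.

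**2. Share of follow-up left voluntary.** Months: 28 − 10 = 18, and 18/28 = 64%. Post-radiation visits fall at months 6, 10, 16, 22 and 28, and the last three of these five are voluntary.

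**3. Late toxicity.** Section 4.2 starts the chronic period 3 months after radiation, at 4 + 3 = month 7. To month 28 that is 21 months. Required follow-up covers 10 − 7 = 3 of them, and 3/21 = 14%.

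**4. The 2-year failure rule.** Two years means month 24 if counted from the start of therapy and month 28 if counted from the end of radiation. The last required visit is month 10, or month 11 with the permitted one-month flexibility. Neither reading can be evaluated from required visits.

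**5. What voluntary attendance could do to the 2-year failure rate.** The documents give no attendance figure, so 50% to 80% at month 28 is an assumption, as is a failure rate of about 10% among attenders. With x failures among m attenders out of 40, the rate in all 40 lies between x/40 and (x + 40 − m)/40.

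| Attendance | m | x | Bounds for all 40 |
|---|---|---|---|
| 80% | 32 | 3 | 7.5% to 27.5% |
| 70% | 28 | 3 | 7.5% to 37.5% |
| 60% | 24 | 2 | 5% to 45% |
| 50% | 20 | 2 | 5% to 55% |

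With full attendance there is no such interval. None of these upper bounds reaches 70%, so in these examples the failure rule would not be met even in the worst case. What is lost is a usable estimate.

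**6. Direction of selection.** Assume a true 2-year failure rate of 15%. If 50% of failures and 80% of other men attend, the observed rate is 0.15 × 0.5 / (0.15 × 0.5 + 0.85 × 0.8) = 9.9%. If 90% and 60% attend, it is 0.15 × 0.9 / (0.15 × 0.9 + 0.85 × 0.6) = 20.9%. If attendance is 70% in both groups, it is 15%.

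**7. The toxicity rule.** 15% of 40 is 6, so more than 15% means at least 7 men. Assume true late Grade 3+ toxicity arising after month 10 of 20%, recorded only in attenders, with attendance unrelated to toxicity and 40 as the denominator. The chance of recording at least 7 is P(X ≥ 7) for X ~ Binomial(40, 0.20 × attendance). It is 71% at full attendance, and 46%, 32%, 20% and 10% at 80%, 70%, 60% and 50%.

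**The case against.** The note may be no more than a loose restatement of the optional late questionnaires. Its next sentence speaks of quality-of-life data, and section 4.2 makes the later questionnaires non-required. On that reading this is a drafting slip rather than a decision to end oncologic follow-up. That is plausible, and it points to the simplest repair, but the note as written covers all follow-up.

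Section 8 says patients should be tested, and it defers to the study calendar. A reader might infer a flat requirement there, which the wording does not support. Section 4.6 and the plain calendar marks carry the contradiction without it.

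A reader might also infer that all progression and late-toxicity data come from men who choose to return, or that the late part of the Grade 3+ rule has no assured data. The calendar does not support either. PSA and toxicity assessment at months 6 and 10 are required of every trial man, so early events and about 3 months of late toxicity are secured.

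Nor do the documents show that censoring is informative. Men with a rising PSA or symptoms might return more often or might go elsewhere, so this is a risk of unknown direction, and steps 5 to 7 rest on assumed figures.

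The stakes are also limited. Section 8 says disease control is not the primary endpoint, and section 9.3 draws no formal conclusions from the Cox comparison of PSA failure. It gives no time horizon for its curves, so the explicit 2-year need comes from section 6.3.

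**Conclusion.** The contradiction stands on the text alone. The calendar note cannot be reconciled with section 4.6 or with the entries marked at months 16, 22 and 28, and it sits badly with section 8. Under the note, 64% of the treatment period and 3 of 5 post-radiation visits are voluntary. The 2-year failure rule has no required data at its own time point, and about 14% of late-toxicity observation to month 28 is assured. These figures assume only the calendar's own month labels. The attendance illustrations show how wide the uncertainty could become and do not predict it.

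The damage is confined to secondary endpoints and safety monitoring. A reader might infer that the primary result is compromised. It is not, because quality of life is assessed at 6 months, inside required follow-up. The comparison with controls has a separate limit: section 4.3 leaves their follow-up to usual care. Required visits would not by themselves secure the metastasis endpoint either, since section 8 leaves screening to the physician.

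**What to change.** **Preferred.** Limit the calendar note to the questionnaires, so that it agrees with section 4.6, section 8 and the optional symbol. State that the entries already marked at months 16, 22 and 28 are required for the trial cohort: PSA, toxicity, current medicines and exam, plus CBC and testosterone where scheduled. Allow PSA and blood results to be taken from the chart or an outside laboratory. Add a record of vital and disease status at those visits, since the calendar has no such row.

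**Controls.** Abstract the same PSA and status data for consenting controls from the medical record, which section 4.3 already permits. Report that controls were not on the protocol visit schedule, because ascertainment may differ between the cohorts.

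**Alternative.** If month 10 is kept as the required end, amend section 4.6 and the calendar to match. State that section 9.3 outcomes beyond month 10 are descriptive in men with available follow-up, and reconcile the 2-year stopping rule with that limit.

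**Cost.** A wording change, one added status record, and some data retrieval for about 40 trial men and about 30 controls. The retrieval is real work: section 4.6 refers to standard practice for follow-up after the 2-year point, so it cannot be cited to show that months 10 to 28 are already covered.
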